6.1. Study Entry

6.1.1. *Volunteer's Informed Consent*

Subjects are informed both in writing and verbally by the investigator before any study-specific procedure is performed. Each volunteer will be informed about the modalities of the clinical study in accordance with the provided volunteer information. The volunteer is given sufficient time (≥ 24 h) to consider participation in the clinical trial and to ask for additional advise if needed. Informed consent from the volunteer will be obtained using a form approved by the responsible EC. The volunteer and informing investigator must each personally date and sign the informed consent form containing an integrated declaration on data privacy protection. The original signed document will be part of the investigator's site file and retained with it, a copy including the insurance policy of the trial will be handed to the volunteer. The informed consent process is documented in the volunteer records.

6.1.2. *Screening*

Screening will be performed within one week (7 days) prior to the administration of the CoVac-1 vaccine. After having signed the informed consent form, volunteers will undergo all assessments listed below:

- Demographics
- Medical history
- Enrolment
- Vital signs
- Physical examination
- Concomitant medications
- Hematology (local lab)
- Blood chemistry and coagulation (local lab)
- Urine analysis (local lab)
- Immunoglobulins/Immunophenotype (local lab), approximately 10 ml blood
- Testing for previous or current SARS-CoV-2 infection: 5ml serum blood will be drawn for antibody testing and a nose/throat swab* will be performed.
- HBV, HCV, HIV-1, (local lab)

- Pregnancy test

* If screening takes more than 48 hours, throat/nose swab for SARS-CoV-2 infection must be repeated. The vaccine can only be applied if a negative SARS-CoV-2 PCR test is available on the day of vaccination not older than 48 hours.

The investigator will review all information obtained from the screening procedures via an eligibility form. The investigator will confirm, in writing, whether the subject fulfils all criteria for eligibility. Volunteers who fulfil all the inclusion criteria and none of the exclusion criteria will be eligible to participate in the trial. Screening failures, i.e. screened volunteers not in compliance with all criteria, are to be excluded and the reason will be recorded in the volunteer records.

Information of volunteer's trial participation can be provided to the volunteer's general practitioner if the volunteer agrees.

6.1.3. *Enrolment*

A volunteer is considered for screening when he or she has signed the Informed Consent form.

In case of confirmation of volunteer's eligibility (volunteers must meet all inclusion criteria and must not meet any exclusion criteria), volunteer will be registered under a specific Vol. ID on a subjects log kept at the trial site. Only these volunteers are enrolled in the study, all others are assessed as screening failures.

The study is open-label.

6.1.4. *Randomisation*

No randomisation will be done in this clinical trial.

6.1.5. *Concomitant Medication and Treatments*

Relevant additional medications and treatments administered to the subjects on entry to the trial or at any time during the trial are regarded as concomitant medications and treatments and must be documented on the appropriate pages of the CRF.

6.1.6. *Permitted Prior and Concomitant Medications and Treatments*

The following concomitant medications and treatments are permitted during the trial.

Part I: No concomitant medication, apart from contraception for FCBP.

Part II : Any concomitant medication (already applied at screening) for e.g. other diseases are allowed except for medications stated in section 6.1.7.

6.1.7. *Prohibited Prior and Concomitant Medications and Treatments*

The following concomitant medications and treatments are prohibited during the trial:

- Immunosuppressive agents apart from (≤ 10 mg prednisolone or equivalent)
- During the trial, other vaccinations or non-urgent medical interventions are prohibited. Initiation of new medications, regardless of indication must be discussed with the investigator and must be noted on the participant's record.

6.1.8. *Contraception*

Within this study, all FCBP must have a negative pregnancy test ≤ 7 days prior initiation of study treatment. A FCBP is defined as any female who does not meet the criteria of non-childbearing potential. These are as follows:

- documented hysterectomy, bilateral oophorectomy (ovarectomy), or bilateral tubal ligation
- post-menopausal (a practical definition accepts menopause ≥ 1 year without menses with an appropriate clinical profile, e.g. age > 45 years in the absence of hormone replacement therapy (HRT). In questionable cases, the subject must have a follicle stimulating hormone (FSH) value > 40 mIU/ml and an estradiol value < 40 pg/ml.

Sexually active men and women of child-bearing potential must use two methods of reliable contraception including one highly effective (Pearl Index < 1) and one additional effective (barrier) method as described below maintained for up to 3 months after the last dose of study therapy.

The following contraceptive methods with a Pearl Index < 1 are regarded as highly-effective:

- oral hormonal contraception ("pill")

Please note: in case that its efficacy is impaired during the trial, e.g. due to vomiting and diarrhoea, additional/other methods as listed below are required to assure adequate safety

- dermal hormonal contraception/contraceptive plaster
- vaginal hormonal contraception (NuvaRing®)
- long-acting injectable contraceptives/implants that release progesterone (Implanon®)
- tubal ligation (female sterilization)
- intrauterine devices that release hormones (hormone spiral)
- double barrier methods

- partner's vasectomy

Additional effective (barrier) methods are:

- male condom
- diaphragm/cervical cap

The following contraceptive methods are not regarded as safe: condom plus spermicide, simple barrier methods (vaginal pessaries, condom, female condoms), copper spirals, rhythm/basal temperature method and withdrawal method (coitus interruptus).

6.2. Vaccination Phase

Vaccination phase begins as soon as possible (within 7 days) after screening and confirmation of patient's eligibility. If screening takes more than 48 hours, throat/nose swab for SARS-CoV-2 infection must be repeated. The vaccine can only be applied if a negative SARS-CoV-2 PCR test is available on the day of vaccination not older than 48 hours.

Peptide vaccines should be injected into the skin at the lower part of the abdomen of the patients. The site of vaccination (right or left) will be determined by the investigator and documented.

To minimize the risk for severe and unexpected side effects for subjects included in the study, all participants will be monitored for at least two hours after vaccination, including close monitoring of heart rate, blood pressure, temperature, oxygen saturation and subjective well-being. Each monitoring unit must be equipped with a crash cart and an intensive care team should be on standby.

Treatment and monitoring of the first volunteer are performed in an in-patient setting with access to intensive care for 24h. Close monitoring (every 30 minutes vital parameters) will be performed for the first four hours after vaccination. Thereafter, monitoring is performed at hourly intervals until 6 hours after vaccination. Thereafter every 3 hours until 24 hours after application of the vaccine.

6.2.1. Visit 1 (Vaccination) (Day 1)

- Signs/symptoms, baseline
- Vital signs, close monitoring after vaccination (blood pressure, temperature, heart rate and oxygen saturation every 30 minutes for at least 2 hours)
- Physical examination, baseline
- Assessment of concomitant medications

- AE assessment
- Hematology and blood chemistry (local lab), approximately 10 ml blood
- Vaccination (section 5.7)
- T-cell response, baseline obtained before vaccination, approximately 60 ml blood
- Serological response, baseline obtained before vaccination, approximately 15 ml blood

6.2.2. *Visit 2 (Day 7 +/- 1)*

- Signs/symptoms, as assessed on volunteer's diary and visit
- Vital signs,
- Physical examination, including investigation of vaccination side
- Assessment of concomitant medications
- AE assessment
- Hematology and blood chemistry (local lab), approximately 10 ml blood
- T-cell response, approximately 60 ml blood
- Serological response, approximately 15 ml blood

6.2.3. *Visit 3 (Day 14 +/- 1)*

- Signs/symptoms, as assessed on volunteer's diary and visit
- Vital signs,
- Physical examination, including investigation of vaccination side
- Assessment of concomitant medications
- AE assessment
- Hematology and blood chemistry (local lab), approximately 10 ml blood
- T-cell response, approximately 60 ml blood
- Serological response, approximately 15 ml blood

6.2.4. *Visit 4 (Interim safety) (Day 28 +/- 2)*

- Signs/symptoms, as assessed on volunteer's diary and visit
- Vital signs,

- Physical examination, including investigation of vaccination site
- Assessment of concomitant medications
- AE assessment
- Hematology and blood chemistry (local lab), approximately 10 ml blood
- T-cell response, approximately 60 ml blood
- Serological response, approximately 15 ml blood

6.2.5. *Visit 5 (End of Safety follow-up = EOS)*

- Signs/symptoms, as assessed on volunteer's diary and visit
- Vital signs,
- Physical examination, including investigation of vaccination site
- Assessment of concomitant medications
- AE assessments
- Hematology and blood chemistry (local lab), approximately 10 ml blood
- T-cell response, approximately 60 ml blood
- Serological response, approximately 15 ml blood

6.2.6. *Visit 6-7 (Follow-up) (Month 3 and 6 +/- 7 days)*

- Medical history, anamnestic evaluation of SARS-CoV-2 specific symptoms
- T-cell response, approximately 60 ml blood
- Serological response, approximately 15 ml blood

6.2.7. *Volunteer's diary/card*

Each patient included in the P-pVac-SARS-CoV-2 study will receive a volunteer's card, which states that he/she is participating in the study (Appendix 13.4). This will also include a 24h emergency contact number. Furthermore, each patient will be provided with a volunteer's diary to note their symptoms daily (Appendix 13.3)

6.2.8. *Unscheduled Visit*

Subjects may contact the investigator at any time for an unscheduled phone or on-site visit should they experience clinical symptoms or signs following injection. At all unscheduled visits, the following minimum assessment will be performed: Questions concerning the history of the present illness as well as the subject's general health and lifestyle. Findings

resulting in (S)AEs will be documented and reported as indicated. All other symptoms/signs will be reported on the next scheduled visit on eCRF.

Upon occurrence of symptoms characteristic of SARS-CoV-2 (i. e. cough, fever (cut-off $>39^{\circ}\text{C}$), loss of taste and smell, limb pain) at any time until day 56, subjects are supposed to get in touch with the investigator. Investigator will initiate SARS-CoV-2 testing for the volunteer (nose or mouth swab followed by PCR per institutional guidelines). If the test is positive, patients should be treated per investigators discretion. Positive results must be recorded as an AESI (section 9.1.4). Negative results will be followed by a second testing $\geq 24\text{h}$ later. Only upon the second negative test, patients are considered negative, all others must be reported as positive.

If participants are positively tested for SARS-CoV-2, all accompanying symptoms and treatments (e.g. hospitalisation, ICU) are recorded

Medically attended AEs and all SAEs will be recorded, and concomitant medication or vaccination will be noted. After identifying the history of the present illness and performing corresponding exams or laboratory tests, the investigator will decide on the best course of treatment according to standard medical practice.

6.3. Assessment of Efficacy

6.3.1. Efficacy Parameters

Immunological Efficacy:

Induction of SARS-CoV-2-specific CD8 $^{+}$ and CD4 $^{+}$ T cells is evaluated using:

- IFN- γ ELISPOT
- Intracellular cytokine staining for TNF and IFN- γ

Induction of SARS-CoV-2 specific antibodies:

- ELISA

6.3.2. Methods and Timing for Assessing, Recording, and Analysing of Efficacy Parameters

Immunological Efficacy:

Serial measurements of immunological efficacy will be performed prior to peptide vaccination (V1), and V2, V3, V4, at the end of study visit and the follow up visits as outlined in table 1. All scheduled visits have a \pm 1 day window unless otherwise stated. 75ml peripheral blood (60 ml Na^+ -heparin and 15 ml serum) for immunological assays will be obtained prior to vaccination as indicated in table 1. Immunological assays will be performed in the Department of Immunology or the Immunopathological Laboratory, Department of Internal Medicine, University Hospital Tuebingen based on standard SOPs.

Amplification of SARS-COV-2-specific T cells:

PBMCs from volunteers are pulsed the respective peptide and cultured for 12 days adding IL-2 on days 3, 5, and 7. Peptide stimulated PBMCs are analyzed by enzyme-linked immunospot (ELISPOT) assay on day 12 or by flow cytometry-based tetramer and intracellular cytokine staining as described below.

IFN- γ ELISPOT assay

IFN- γ ELISPOT assays are carried out as described previously.⁸⁸ In brief, 96-well nitrocellulose plates are coated with anti-IFN- γ . Plates are blocked and PBMCs (ex vivo or after T-cell amplification as described above) are distributed to the wells and re-stimulated with HLA class II peptides. Cytokine staining is performed after incubation period. Analysis is performed according to manufacturer's instructions. Spots are counted using an Immunospot analyzer (according to the cancer immunoguiding program (CIP) guidelines).⁸⁹

To differ between vaccine induced and natural T-cell induction by SARS-CoV-2 infection we will include, beside the T-cell epitopes included in the CoVac-1 vaccine, additional SARS-CoV-2 T-cell epitopes defined in our preclinical work in the peptide readout²⁴.

Cellular conversion rate (CCR) is calculated by dividing the number of volunteers with an immune response by the number of tested participants to a time point (Visit 2, 3, 4 and 5). A volunteer is considered as having developed an immune response due to immunization if ex vivo IFN- γ ELISPOT assay is positive (as described above) and the spot count is at least 2-fold higher than the baseline assay (Visit 1).

Intracellular IFN- γ and TNF staining

The frequency and functionality of peptide-specific CD8 $^+$ T cells is analyzed by intracellular IFN- γ or TNF staining as described previously.^{88 90} PBMCs are pulsed with individual peptide and incubated in the presence of Brefeldin A and GolgiStop. Cells are labeled using

Cytofix/Cytoperm, CD8, CD4, TNF and IFN- γ coupled to fluorochromes. Samples are evaluated on a FACS analyzer.

Enzyme-linked immunosorbent assay (ELISA)

To identify SARS-CoV-2 antibody responses induced by the vaccine, ELISA assays will be performed using serum samples (15 ml serum tube) obtained at the time points described in Table 1. Specific antibodies against the seven SARS-CoV-2 T-cell epitopes will be assessed by ELISA assay at the Department of Immunology, Tübingen. To differ between vaccine induced antibody response additional standard Elecsys® Anti-SARS-CoV-2 assay supplied by F. Hoffmann-La Roche AG, Basel, Switzerland or ADVIA Centaur SARS-CoV-2 Total (COV2T) (Siemens Healthcare Diagnostics GmbH) will be performed at central laboratory of the University Hospital Tuebingen.

Occurrence or relevant (≥ 2 -fold) increase of SARS-CoV-2 specific IgG antibodies compared to baseline are considered as positive.

In the unlikely event of antibody induction by the CoVaC-1 vaccine, neutralization capacity of antibodies will be assessed by SARS-CoV-2 Pseudovirus Neutralization Assay (CD, Creative Diagnostics®)

6.4. Assessment of Safety

6.4.1. Safety parameters

(Serious) Adverse Events (see section 9)

- Vital signs: pulse, blood pressure, temperature, and weight
- Physical examination including inspection of the vaccination site
- Clinical laboratory evaluations:
 - Hematology: white blood cell (WBC), hemoglobin (Hb), platelet count, absolute neutrophil count (ANC), absolute lymphocyte count (ALC)
 - Chemistry: AP, total bilirubin, AST/ SGOT, ALT/ SGPT, LDH, and uric acid, CRP, sodium, potassium, calcium, blood urea nitrogen, creatinine, glucose, C-reactive protein
- Concomitant medications
- (S)AEs by NCI CTCAE Version 5.0 and as in appendix 14.5

6.4.2. Methods and Timing for Assessing, Recording, and Analysing Safety Parameters

Serial measurements of safety will be performed at screening and at scheduled intervals throughout the duration of the study as outlined in table 1. All scheduled visits have a \pm 1 day window unless otherwise stated. Abnormalities will be captured as protocol deviations. Lab abnormalities grade 1-2 are only considered AE if they fulfill one of the following criteria:

- Accompanied by clinical symptoms.
- Requiring a change in concomitant therapy (e.g. addition or change in a concomitant medication, therapy or treatment).

All Grade 3-4 laboratory abnormalities fulfilling the criteria for an SAE will be reported as SAEs and will be recorded on the AE pages of the CRF; however, those that are not deemed by the investigator to be part of a diagnosis or syndrome will not be reported to the Health Authorities in an expedited manner. Cause of death is to be recorded in the CRF and the subject's medical record.

6.5. Vaccination holding rules

Safety holding rules for each subject will apply throughout the study period until interim safety analysis (V4). Vaccination of further study subjects in the consecutive study phase will not occur until a safety review has been conducted by the DSMB and only by approval a holding rule can be resolved. If a holding rule is activated, the PI will inform the Sponsor within 48 hours. The Sponsor will inform the responsible authorities (PEI and EC).

If the DSMB permits the resumption of injections, a formal request with pertinent data must be submitted to ECs and PEI. The discontinuation of a holding rule should be communicated to all entities in the same manner and timeframe as described above.

The DSMB safety review will consider:

- The relationship of the AE or SAE to the vaccine or other possible causes of the event.
- If appropriate, additional screening or laboratory testing for other volunteers to identify those who may develop similar symptoms and alterations to the current informed consent form will be discussed.

All injected volunteers will be followed for safety until resolution or stabilization (if determined to be chronic sequelae) of their AE.

The holding rules are as follow:

- Solicited local ADRs: If more than 30% of injections are followed by Grade ≥ 3 solicited swelling or pain or Grade 4 redness (first occurrence at any time after vaccination) and persisting at Grade 3 (swelling or pain)/4 (redness) for > 48 h to maximum 72 hours depending upon symptom severity and kinetics.
- Solicited systemic AEs: If more than 25% of injections are followed by Grade 3 solicited systemic AE beginning within 3 days after study injection (day of injection and 2 subsequent days) and persisting at Grade ≥ 3 for > 48 h to maximum 72 hours depending upon symptom severity and kinetics.
- Unsolicited AEs: If more than 25% of volunteers develop a Grade ≥ 3 unsolicited AE (including laboratory AE and physical observations) that is considered probably or definitely related to injection and persists at Grade 3 for > 48 to maximum 72 hours depending upon symptom severity and kinetics.
- A suspected unexpected serious adverse drug reaction (SUSAR) occurs that is life-threatening or results in death.

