6.4.2. Methods and Timing for Assessing, Recording, and Analysing Safety Parameters

Serial measurements of safety will be performed at screening and at scheduled intervals throughout the duration of the study as outlined in table 1. All scheduled visits have a \pm 1 day window unless otherwise stated. Abnormalities will be captured as protocol deviations. Lab abnormalities grade 1-2 are only considered AE if they fulfill one of the following criteria:

- Accompanied by clinical symptoms.
- Requiring a change in concomitant therapy (e.g. addition or change in a concomitant medication, therapy or treatment).

All Grade 3-4 laboratory abnormalities fulfilling the criteria for an SAE will be reported as SAEs and will be recorded on the AE pages of the CRF; however, those that are not deemed by the investigator to be part of a diagnosis or syndrome will not be reported to the Health Authorities in an expedited manner. Cause of death is to be recorded in the CRF and the subject's medical record.

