6.5. Vaccination holding rules

Safety holding rules for each subject will apply throughout the study period until interim safety analysis (V4). Vaccination of further study subjects in the consecutive study phase will not occur until a safety review has been conducted by the DSMB and only by approval a holding rule can be resolved. If a holding rule is activated, the PI will inform the Sponsor within 48 hours. The Sponsor will inform the responsible authorities (PEI and EC).

If the DSMB permits the resumption of injections, a formal request with pertinent data must be submitted to ECs and PEI. The discontinuation of a holding rule should be communicated to all entities in the same manner and timeframe as described above.

The DSMB safety review will consider:

- The relationship of the AE or SAE to the vaccine or other possible causes of the event.
- If appropriate, additional screening or laboratory testing for other volunteers to identify those who may develop similar symptoms and alterations to the current informed consent form will be discussed.

All injected volunteers will be followed for safety until resolution or stabilization (if determined to be chronic sequelae) of their AE.

The holding rules are as follow:

Protocol		
Protocol code and Short Title:	P-pVAC-SARS-CoV-2	Date/Version:08.03.2021/V1.4

- **Solicited local ADRs:** If more than 30% of injections are followed by Grade ≥ 3 solicited swelling or pain or Grade 4 redness (first occurrence at any time after vaccination) and persisting at Grade 3 (swelling or pain)/4 (redness) for > 48 h to maximum 72 hours depending upon symptom severity and kinetics.
- **Solicited systemic AEs:** If more than 25% of injections are followed by Grade 3 solicited systemic AE beginning within 3 days after study injection (day of injection and 2 subsequent days) and persisting at Grade ≥ 3 for > 48 h to maximum 72 hours depending upon symptom severity and kinetics.
- **Unsolicited AEs:** If more than 25% of volunteers develop a Grade ≥ 3 unsolicited AE (including laboratory AE and physical observations) that is considered probably or definitely related to injection and persists at Grade 3 for > 48 to maximum 72 hours depending upon symptom severity and kinetics.
- A suspected unexpected serious adverse drug reaction (SUSAR) occurs that is life-threatening or results in death.

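### In section 6.5 the entry grade and the persistence grade disagree in all three graded holding rules, so a more severe reaction can lower the hold count

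*Supplement*

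**What the plan says.** Section 6.5 of V1.4 lists three frequency-based holding rules defined by grade, and one single-event rule.

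- **Local rule.** The threshold is "If more than 30% of injections are followed by" a qualifying reaction. Entry is Grade 3 or higher for swelling or pain and Grade 4 for redness. The duration clause is "and persisting at Grade 3 (swelling or pain)/4 (redness) for > 48 h".
- **Systemic rule.** The threshold is more than 25% of injections. Entry is Grade 3, with onset within 3 days. The duration clause is "and persisting at Grade ≥ 3 for > 48 h to maximum 72 hours".
- **Unsolicited rule.** The threshold is more than 25% of volunteers. Entry is Grade 3 or higher, and the rule expressly takes in laboratory events. The duration clause is "that is considered probably or definitely related to injection and persists at Grade 3 for > 48 to maximum 72 hours".
- **Single-event rule.** One life-threatening or fatal SUSAR activates a hold.

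Two other parts of the protocol bear on the point. Sections 8.2 and 8.6 make one SAE associated with CoVac-1 the formal stopping rule. Section 6.4.2 states "All Grade 3-4 laboratory abnormalities fulfilling the criteria for an SAE will be reported as SAEs", so a Grade 4 laboratory value is not an SAE merely because of its grade.

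**The concern.** A frequency-based hold should never become harder to reach because reactions are worse. Here it can. The list uses Grade 3 and Grade 3 or higher as different expressions. Sections 9.3.2 and 14.5 define Grade 4 separately from Grade 3. No sentence says that persisting at Grade 3 means persisting at Grade 3 or above.

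A stable Grade 3 swelling lasting 50 h is therefore counted. A swelling at Grade 3 for 24 h and at Grade 4 afterwards is not.

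The graded rules exist to pick up clusters of severe reactions that are not individually serious. Section 9.4.1 also has the DSMB informed when a holding rule is reached, so a missed count loses that trigger too. Part II enrols volunteers aged 56 to 80, with or without pre-existing conditions, after a Part I in healthy adults aged 18 to 55.

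**Working it through.** **Step 1: set the clauses of section 6.5 side by side.**

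| Rule | Entry grade | Persistence grade | Match? |
|---|---|---|---|
| Local, swelling or pain | ≥ 3 | 3 | no |
| Local, redness | 4 | 4 | yes |
| Systemic | 3 | ≥ 3 | no |
| Unsolicited | ≥ 3 | 3 | no |

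**Step 2: apply each rule literally to possible courses.**

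- Swelling, pain or unsolicited, Grade 3 for more than 48 h: counted, whether or not it worsens later.
- Swelling, pain or unsolicited, Grade 3 for less than 48 h and then Grade 4: entry met, persistence failed, not counted.
- Swelling, pain or unsolicited, Grade 4 throughout: entry met, persistence failed, not counted.
- Systemic, Grade 4 from onset: entry failed, not counted. By Appendix 14.5 this is narrow. Most systemic symptoms have no Grade 4, and fever reaches it only by lasting, so vomiting and diarrhoea remain.

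**Step 3: find the counts needed.** Section 6.5 does not say whether the denominator is the part or the whole trial. I take Part II (24 in the synopsis) and show 36 as the alternative. The smallest count strictly above the threshold is floor(threshold × n) + 1.

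- Local, n = 24: floor(7.2) + 1 = 8. One uncounted Grade 4 reaction turns 8/24 = 33.3% into 7/24 = 29.2%: no hold.
- Unsolicited, n = 24: floor(6.0) + 1 = 7. One uncounted event turns 7/24 = 29.2% into 6/24 = 25.0%, which is not more than 25%: no hold.
- With n = 36 the counts are 11 and 10. Losing one gives 10/36 = 27.8% and 9/36 = 25.0%: again no hold.

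**Step 4: illustrate the effect on the chance of a hold.** The protocol states no operating characteristic for the holding rules, so there is no figure to reproduce. Let p be the true rate of persisting Grade ≥ 3 reactions and g the share of them that the literal wording drops. Both are assumptions. Then P(hold) = P(X ≥ k) with X ~ Binomial(24, p(1 − g)).

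| Rule | p | g = 0 | g = 10% | g = 25% | g = 50% |
|---|---|---|---|---|---|
| Local, k = 8 | 30% | 0.435 | 0.310 | 0.152 | 0.020 |
| Local, k = 8 | 40% | 0.808 | 0.680 | 0.435 | 0.089 |
| Local, k = 8 | 50% | 0.968 | 0.914 | 0.732 | 0.234 |
| Unsolicited, k = 7 | 30% | 0.611 | 0.482 | 0.285 | 0.057 |
| Unsolicited, k = 7 | 40% | 0.904 | 0.818 | 0.611 | 0.189 |
| Unsolicited, k = 7 | 50% | 0.989 | 0.964 | 0.855 | 0.393 |

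These figures overstate the practical loss, because they give no credit to the one-SAE stop. They apply to dropped events that are not classed as serious.

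**Step 5: check the backstops.** For events that are classed as serious, section 8.1.1 gives 81.6% power to see at least one in 33 at a 5% rate. This reproduces: 1 − 0.95^33 = 0.816. So a single related serious event stops recruitment long before 7 or 8 reactions accumulate. The backstop does not work for events not classed as serious. Section 6.4.2 leaves room for such Grade 4 laboratory values. Grade 4 swelling in Appendix 14.5 is necrosis, which is not a named criterion in section 9.1.5 and would depend on the medically significant clause.

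**The case against.** The strongest case against is that other rules already cover most of the gap.

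- Section 9.3.2 defines Grade 4 by life-threatening consequences, and Grade 4 pain in Appendix 14.5 includes hospitalisation. The SAE definition in section 9.1.5 takes in both, as well as medically important events that may need intervention. A typical related Grade 4 reaction would therefore stop the trial at the first case. This stands, and it sets the size of the point.
- The wording may simply be loose. The systemic rule mismatches in the opposite direction, which suggests that the two expressions were used interchangeably, and a DSMB might read persistence at Grade 3 as not having fallen below it. That is plausible, but the text does not say so, and a rule that triggers a safety hold should not depend on it.
- Other routes exist. Section 1.4 allows an emergency DSMB meeting at any time, section 9.4.1 has the DSMB informed of safety-relevant events, and section 8.6 lets the sponsor terminate the trial. These stand, but they are discretionary.
- Section 6.5 speaks of withholding vaccination in the consecutive phase, V1.4 has no phase after Part II, and section 3 has Part II volunteers treated simultaneously. How far a count in Part II would change vaccination is therefore uncertain. This also stands.

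A reader might infer something stronger: that any number of necrotic reactions would pass unnoticed, or that the hold fails exactly when reactions are worst. The documents do not support that. Appendix 14.5 also lists necrosis under Grade 3 in the erythema and pain rows, so a painful necrotic reaction could be counted through the pain row. Section 9.1.2 calls the appendix guidance only. The one-SAE stop also remains in force. Nor does anything show that Grade 4 was left out on purpose.

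**Conclusion.** The point holds as a wording inconsistency in a stated decision rule, and it affects all three graded bullets. The systemic rule is not a sound model for the other two, because it has the mirror fault. Redness is unaffected, and a reaction that spends more than 48 h at Grade 3 before worsening still counts.

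Read literally, one reaction that is too severe to be counted is enough to miss a hold at the threshold: 29.2% against more than 30%, or 25.0% against more than 25%. This rests on the literal reading and on the assumed denominator, although 36 gives the same result as 24.

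The practical gap is limited. It consists mainly of related Grade 4 events judged non-serious, such as some laboratory events or local reactions, occurring alongside enough other Grade 3 reactions to bring a rule near its threshold. Section 1.1.5.1 reports granuloma of at most Grade 2 in Part I and other local events as mild, so the event rates in the illustration are hypothetical. The correction should still be made, because it concerns a safety rule and costs almost nothing.

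**What to change.** Reconcile the entry grade and the persistence grade within each of the local, systemic and unsolicited bullets of section 6.5, and across the three. The test of the new wording is that a reaction cannot lose its count by being more severe, whether at onset or by worsening. Which grade applies is for the sponsor and the DSMB to set; none is proposed here.

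The cost is an edit to three bullets in one section, with no new data, visits or assessments. The downside is that a hold may trigger slightly more often.
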